10.8 Sample Size Justification

No formal hypotheses are being tested in this study and hence a target sample size of 40 patients

is deemed adequate for a preliminary investigation of the feasibility of this procedure, as well as for providing sufficient information for appropriately sizing a subsequent study.

10.9 Analyses to be Conducted

Analyses described below will be performed on the pooled set of 40 patients [REDACTED]

Disposition of Study Patients

Patient disposition will be summarized using counts and percentages. The number and percentage of patients completed and discontinued along with the specific reasons for discontinuation will be tabulated by treatment group and in total.

Demographic and Baseline Characteristics

Summary statistics will be provided for patient demographics and pre-operative ablation characteristics.

Primary and Secondary Endpoint Analyses

Device user experience feedback will be collected from the treating physician who will complete the User Experience Survey following each ablation procedure. The questionnaire will focus on procedure workflow and the user's assessment on ease/difficulty of using the device. Summary statistics will be provided for each question.

The number and percentage of patients achieving technical success will be summarized and a 95% confidence interval will be estimated. Technique efficacy, as well as primary and secondary efficacy rates and hospital readmission rates, will be summarized in a similar manner. Local soft tissue lesion recurrence rates will be estimated using the Kaplan-Meier method and 95% confidence intervals will be provided.

The number and percentage of patients experiencing AEs from the start of ablation (Visit 2A) to Visit 3 (the first post-ablation visit) will be summarized by MedDRA preferred term and system organ class. A similar summary will also be provided for device related and procedure related, and all SAEs. Ninety-five percent confidence intervals may be provided for pre-specified adverse events of interest [REDACTED]

[REDACTED]

[REDACTED]

[REDACTED]

[REDACTED]

[REDACTED]

[REDACTED]

[REDACTED]

[REDACTED]

[REDACTED]

[REDACTED]

Similar summaries will also be provided for the entire observation period from the ablation procedure date through 1 year of follow-up.

The EORTC QOL questionnaires and Numeric Pain Rating Scale scores will be summarized with methodology consistent to the recommendations of the specific survey. Additional endpoints will be summarized with descriptive statistics.

Plans for Interim Analysis

There are no plans for interim analyses, whose intent would be to stop the study early or to modify the study design. Two analysis timepoints are planned. The first analysis will occur after all patients within a treatment group (interventional pulmonologist or thoracic surgeon) complete Visit 3 (30 days ± 7 days after the first ablation procedure). The analysis will provide a summary of the User Experience Survey, technical success, technique efficacy, and safety through Visit 3. When the second group completes this timepoint, results will be summarized for that group and subsequently in total. The second analysis timepoint will be at the completion of the study.

Ongoing Review

[REDACTED]

The Sponsor will also review complications periodically, as per the Safety Management Plan.

[REDACTED]

[REDACTED]

A report of death will stop enrollment and require an investigation to determine if the death is related to the ablation procedure. If the death is deemed not related to the ablation procedure the study may resume enrollment.

Data Safety Monitoring Board

A Data Safety Monitoring Board (DSMB) will be appointed by the Sponsor to review, on a regular basis, safety data from the study. The DSMB will advise the Sponsor regarding the continuing safety of patients and those yet to be recruited to the study. Based on accumulating data from the study, the DSMB may recommend whether to continue, suspend, modify, or stop the study.

At the conclusion of the review of all 40 patients, the DSMB will also give a final assessment of the safety of the procedure. The composition, responsibilities, frequency of DSMB meetings, handling of emergency situations, and documentation of DSMB meetings is specified in the DSMB Charter.

Analysis of Safety

The analysis of safety is summarized above under Primary and Secondary Endpoint Analyses.

Handling of Dropouts or Missing Data

All analyses will be performed only on patients undergoing ablation with the flexible probe and only observed data will be analyzed. There will be no imputation of missing data for any parameters or for early terminated patients.

Multicenter Studies

No adjustment for center is planned in the statistical analysis. However, center specific analyses may be conducted pending within-center sample size to understand the effect that surgeon techniques and site's SOC may have on the overall results.

[REDACTED]

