9.6 Safety Analyses

Safety will be assessed through the incidence of AEs and SAEs, which will be coded using MedDRA. The number and percentage of subjects reporting AEs and SAEs will be summarized at the MedDRA system organ class and preferred term level. Similar summaries will also be provided for AEs and SAEs related to the study device, as well as for AEs and SAEs related to the study procedure. Related events are those where the relationship is indicated as Unlikely, Possibly, Probably, or Causal. Summaries of all AEs and SAEs reported within the first 30 days after the initial ablation procedure will be generated. All reported adverse events will be listed.

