9.9 Handling of Missing Data

All summaries will be performed only on subjects who receive ablation through the flexible probe. There will be no imputation of data for early terminated subjects or for missing data within the database.

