System Organ Class 4	Preferred Term 1	xx (xx.x%)
	Preferred Term 2	xx (xx.x%)

The following tables will have the same format as Table 14:

Table 15	Serious Adverse Events by System Organ Class and Preferred Term Full Analysis Set
Table 16	Adverse Events Related to the Study Device by System Organ Class and Preferred Term Full Analysis Set
Table 17	Serious Adverse Events Related to the Study Device by System Organ Class and Preferred Term Full Analysis Set
Table 18	Adverse Events Related to the Study Procedure by System Organ Class and Preferred Term Full Analysis Set
Table 19	Serious Adverse Events Related to the Study Procedure by System Organ Class and Preferred Term Full Analysis Set
Table 20	Adverse Events Related to the Study Device Within 30 Days of the Initial Ablation Procedure by System Organ Class and Preferred Term Full Analysis Set
Table 21	Serious Adverse Events Related to the Study Device Within 30 Days of the Initial Ablation Procedure by System Organ Class and Preferred Term Full Analysis Set

Table 22
 Target Lesion Details – Independent Reviewer
 Full Analysis Set

Characteristics	Overall (N = ##)
Lesion Location	
RUL	xx (xx.x%)
RML	xx (xx.x%)
RLL	xx (xx.x%)
LUL	xx (xx.x%)
LLL	xx (xx.x%)
Other	xx (xx.x%)
Distance from Pleura (cm)	
n	xx
Mean	xx.x
Standard Deviation	x.xxx
Median	xx.x
Minimum, Maximum	xx.x, xx.x
Largest Diameter (cm)	
n	xx
Mean	xx.x
Standard Deviation	x.xxx
Median	xx.x
Minimum, Maximum	xx.x, xx.x
Smallest Diameter (cm)	
n	xx
Mean	xx.x
Standard Deviation	x.xxx
Median	xx.x
Minimum, Maximum	xx.x, xx.x
Ablation Margin, Smallest Diameter (cm)	
n	xx
Mean	xx.x
Standard Deviation	x.xxx
Median	xx.x
Minimum, Maximum	xx.x, xx.x

Table 22
Target Lesion Details – Independent Reviewer
Full Analysis Set

Characteristics	Overall (N = ##)
Technical Success – Visit 2A/Day 0	
Yes	xx (xx.x%)
95% Exact Confidence Interval	xx.x%, xx.x%
Technique Efficacy at Day 30	
Yes	xx (xx.x%)
95% Exact Confidence Interval	xx.x%, xx.x%
Target Lesion Recurrence Day 30 to Month 12	
Yes	xx (xx.x%)
95% Exact Confidence Interval	xx.x%, xx.x%

The following listings will be generated for this study:

Listing 1	Inclusion/Exclusion Criteria All Subjects
Listing 2	Inclusion/Exclusion Criteria – Ablation Visit All Subjects
Listing 3	Study Visits All Subjects
Listing 4	Study Visit Details All Subjects
Listing 5	Demographics All Subjects
Listing 6	Pregnancy Test All Subjects
Listing 7	Medical History All Subjects
Listing 8	Surgical History All Subjects

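### With no imputation allowed and no rule for unclassified events, an adverse event whose relationship field is blank drops out of the related-event tables, which can only understate related harm

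*Protocol*

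**What the plan says.** **Missing data.** Protocol 10.9 (Handling of Dropouts or Missing Data) says that "only observed data will be analyzed" and then: "There will be no imputation of missing data for any parameters or for early terminated patients". SAP 9.9 carries this over: "There will be no imputation of data for early terminated subjects or for missing data within the database". Neither passage sets AE classification fields apart.

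**Related events.** SAP 9.6 defines them by a positive entry: "Related events are those where the relationship is indicated as Unlikely, Possibly, Probably, or Causal". It does not say what happens when nothing is entered.

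**Early events.** SAP 9.6 promises: "Summaries of all AEs and SAEs reported within the first 30 days after the initial ablation procedure will be generated". The only 30-day shells are Tables 20 and 21, and both are limited to device-related events; Table 20 is titled "Adverse Events Related to the Study Device Within 30 Days of the Initial Ablation Procedure by System Organ Class and Preferred Term". (The gap between that promise and the shells is a separate matter.) No passage says how an event with an incomplete onset date is placed.

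**All events.** Tables 14 and 15 follow from "The number and percentage of subjects reporting AEs and SAEs will be summarized at the MedDRA system organ class and preferred term level" and need neither relationship nor date. SAP 9.6 adds: "All reported adverse events will be listed".

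**The concern.** In most tables, leaving a missing value missing is neutral, because the subject drops out of numerator and denominator together. An AE table works differently. The shells show subjects with an event over the Full Analysis Set N, so an event that cannot be classified becomes a non-event while its subject still counts below the line. The effect has one direction: related counts can fall but not rise.

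It also fits poorly with the SAP's own choice. Section 9.6 takes a broad view and counts even Unlikely as related. On a literal reading, an event of unknown relationship is then treated as less related than one judged Unlikely.

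The reader of a table would not see the loss. The QLQ-LC13 shell (Table 13) has a row for no response, but the AE shells have neither a row nor a footnote for a missing relationship.

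Device-related, procedure-related and serious AEs make up the first-listed secondary endpoint (Protocol 6.2). This is a first-experience study whose enrolment was halted after a death (opening of the SAP) and ended at 10 treated subjects (SAP 7).

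**Working it through.** The plan gives no AE rate, no missing-field rate and no figure to reproduce. The check has four steps.

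**1. Which tables depend on which field** (SAP 9.6 and Appendix)

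| Field missing | Tables the event leaves, read literally | Where it stays |
|---|---|---|
| Device relationship | 16, 17, 20, 21 | 14, 15, Listing 29 |
| Procedure relationship | 18, 19 | 14, 15, Listing 29 |
| Onset date incomplete | 20, 21, and only if the date cannot be resolved | 14, 15, Listing 29, and 16–19 as applicable |

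Tables 15, 17, 19 and 21 are the serious-event versions, so they are affected only if the event is serious.

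**2. Size per affected subject.** N = 10 (SAP 7). A subject leaves a row only if the blank event is that subject's sole qualifying event for the row. Each such subject moves the rate by 1/10 = 10 points; at the planned N = 40 it would have been 1/40 = 2.5 points. Exact (Clopper–Pearson) 95% intervals at N = 10, for scale only because the AE shells print none:

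- 0/10: 0% (0 to 30.8)
- 1/10: 10% (0.3 to 44.5)
- 2/10: 20% (2.5 to 55.6)

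One blank could therefore turn 2/10 into 1/10, or 1/10 into 0/10.

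**3. How likely a loss is, under assumed rates.** Let p be the true proportion of subjects with a qualifying event and m the share of those whose qualifying event has a blank field. Both are assumptions. Treating subjects as independent, P(at least one subject lost) = 1 − (1 − p·m)^10.

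| m | p = 0.1 | p = 0.3 |
|---|---|---|
| 0 | 0% | 0% |
| 5% | 4.9% | 14.0% |
| 10% | 9.6% | 26.3% |
| 20% | 18.3% | 46.1% |

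For example, with p = 0.3 and m = 10%: 1 − 0.97^10 = 26.3%.

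**4. How far incomplete dates matter.** Suppose only month and year of onset are known. For each of the 365 ablation dates in a non-leap year, ask whether onset can be placed inside or outside Days 0–30 without imputing anything. AE collection starts at ablation (Protocol 12.2).

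- Onset in the ablation month: inside for 365 of 365.
- Onset in the next month: unresolved for 351 of 365 (7 inside, 7 outside).
- Onset two months on: outside for 363 of 365 (2 unresolved).

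The date problem is confined almost entirely to next-month onsets and to dates with no month, and it touches Tables 20 and 21 only.

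**The case against.** The strongest reply is that the plan is silent rather than wrong. No passage says that a blank relationship means not related. Counting a blank as related could be called a classification convention, which SAP 9.9 neither adopts nor forbids. That is fair. But the analyst would then have to choose a convention with open-label data in view, and the definition in SAP 9.6 points towards exclusion. The same sentence is needed either way.

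Second, blanks should be rare. Relationship is the investigator's own judgement and is to be recorded for device and procedure separately (Protocol 12.2). Forms have deadlines, and data queries and casebook sign-off follow (Protocol 9.1). This stands as a limit on size. It does not exclude blanks, because Protocol 12.2 lets the investigator's assessment of a serious event be added to the form after the first report.

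Third, with 10 subjects and a full listing, nothing is hidden. This also stands: a reader of Listing 29 could find each blank. A reader of the tables alone could not.

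A reader might infer more than the documents support:

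- **That related harm is in fact undercounted.** No missing rate is given, so this is a possibility only.
- **That any event dated only to a month falls out of the 30-day tables.** Step 4 shows that most such dates can be placed. SAP 9.6 also speaks of events reported within 30 days and does not name onset date.
- **That recall between Visit 3 and Visit 4 puts early events at risk.** That gap lies almost wholly after Day 30. Even if Visit 3 falls on Day 23, only Days 24–30 are exposed: 7 days of a gap of about 129 (152 − 23) to 190 (213 − 23) days, taking 5 and 7 months as 152 and 213 days.

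**Conclusion.** The point holds for the relationship fields, as a low-cost improvement rather than a threat to the study's conclusions. Read literally, the no-imputation rule and the definition of related together remove unclassified events from Tables 16–21, device and procedure separately, in the favourable direction only. For dates it holds in a small part of Tables 20 and 21. Total AE and serious AE counts are untouched.

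The size is 10 points per affected subject at N = 10, and zero if no field is blank at lock. The conclusion assumes that SAP 9.6 is programmed as worded and that at least one blank survives querying; the documents settle neither.

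**What to change.** In SAP 9.6 and 9.9:

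1. Exempt AE classification from the no-imputation rule.
2. Count a missing device relationship as device-related and a missing procedure relationship as procedure-related.
3. For Tables 20 and 21 only, count an incomplete onset date as within 30 days unless the known date parts, the resolution date or the visit of first report indicate a later onset. An undated event first reported at Visit 4 and not present at Visit 3 is then not early. Without the visit of report, the rule would wrongly add such events to the early count.
4. Footnote each affected table with the number of events classified by these rules, and keep raw values in the listings.

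The cost is a few sentences and a few lines of programming. The rule for dates needs the visit or date of first report; the AE form is not among the documents, so its availability should be confirmed. The downside is that related or early AE counts may come out slightly less favourable. If no record is incomplete, every table is unchanged and the footnotes read zero.

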11.0 RISKS AND BENEFITS OF THE STUDY

This study may or may not provide any benefits to the patient. However, the data collected throughout the study may help to assess the efficacy and safety of a new treatment technique: transbronchial microwave ablation of soft tissue lesions of the lung. As described in the Introduction, retrospective studies of patients who underwent percutaneous microwave ablation of the lung as far back as 2003 have provided data that the percutaneous route of treatment has been safe and effective. Transbronchial microwave ablation of soft tissue lesions represents a new approach that has not been routinely used in clinical practice, so there may be some unforeseeable and unknown risks associated with this technique in this study.

12.0 ADVERSE EVENTS

12.1 Definitions

Adverse Event

For this study, an adverse event is defined as any undesirable clinical occurrence in a patient. All AEs, whether attributable to the device/procedure or not, are to be recorded in the eCRF and reported to the Sponsor.

Expected Morbidity/Anticipated Adverse Events

An expected morbidity/procedural complication is defined as an AE that is known to be common or usual in nature, severity, or incidence during ablation of the lung.

Serious Adverse Event

It is the Investigator's responsibility to determine the "seriousness" of an AE using the protocol defined terms below. An SAE is an AE that results in one or more of the following for this study:

- Life-threatening: The patient was at imminent risk of dying at the time of the adverse event.
- Permanent Impairment: An AE that resulted in permanent impairment of a body function or permanent damage to a body structure.
- Necessitated Intervention: An AE that resulted in a condition that necessitated medical or surgical intervention to preclude permanent impairment of a body function or damage to a body structure.
- Required in-patient or prolonged hospitalization.
- A persistent or significant disability or incapacity.
- Resulted in death: An AE that resulted in the patient's death

Notes:

1. Progression of the disease under study should not be reported as an SAE.
2. "Death" should not be reported as an AE. The cause of death should be reported as an SAE. The only exception is "Sudden Death" when the cause is unknown.
3. Planned hospitalization for a pre-existing condition is not considered an SAE.
4. A procedure required by the protocol is not considered an SAE, unless the patient experiences a serious deterioration in health or hospitalization is prolonged.

The Sponsor will review all reported AEs and SAEs according to the current Safety Monitoring Plan.

Severity of Adverse Events

It is the Investigator's responsibility to assess the severity of an AE. A change in severity may constitute a new reportable AE.

The severity of each AE will be determined via the Common Terminology Criteria for Adverse Events (CTCAE) version 5.0. The CTCAE may be accessed here: https://ctep.cancer.gov/protocolDevelopment/electronic_applications/ctc.htm.

Also, the following guideline should be used to determine the severity of each AE:

- **MILD:** Awareness of signs or symptoms, but does not interfere with the patient's usual activity, or is a transient event that resolves without treatment and with no sequelae.
- **MODERATE:** A sign or symptom, which interferes with the patient's usual activity.
- **SEVERE:** Incapacity with inability to do work or usual activities.

Relationship of Adverse Events

It is the Investigator's responsibility to assess the relationship between all AEs and the study procedure.

The following guidelines should be used in determining the relationship of an AE to a device, study procedure, or other causality:

Not related	Temporal sequence between device usage and the event is such that the relationship is unlikely.
Unlikely related	Temporal sequence between device usage and the event is such that the relationship is not unlikely or the subject's condition or concomitant therapy could have caused the AE.
Possibly related	Temporal sequence is relevant or the event abates upon device usage completion or the event cannot be reasonably explained by the patient's condition.
Probably related	Temporal sequence is relevant and the event abates upon product device usage or reappearance of the event on repeat device usage (re-challenge).
Causal relationship	Temporal sequence between device usage and the event is such that the relationship is unlikely.

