12.2 Reporting Adverse Events

The Investigator is required to report all AEs experienced by the patient from the start of the ablation procedure (Visit 2A) until the patient completes Visit 5 (1 year after the first ablation procedure) or withdraws early (prior to Visit 5) to the Sponsor within 14 days of become aware of the AEs. All AEs (both serious and non-serious) must be reported in the AE eCRF. The Investigator will evaluate the severity of the event and its relatedness to the study device or procedure.

Any necessary medical management of the event will be recorded in the patient's medical record/source document. All AEs must be followed until resolution or until they become stable.

The Investigator will record all AEs (both serious and non-serious) in the source documents. CTC (Common Terminology Criteria) should be used when recording AEs. In addition, the following information should be recorded:

- Onset date
- Resolution date or date of death
- Severity of the event using CTCAE
- Action taken
- Event status (ongoing at study end or resolved)
- Relationship of AE to the ablation device used in the study
- Relationship of AE to the study procedure
- Indication of seriousness.

Data related to SAEs will be collected until event resolution, or until the event is considered stable, or until all attempts to determine the resolution of the event are exhausted. All AEs that are unresolved at study completion (or early termination) will be recorded as ongoing at study end.

Reporting Serious and Non-Serious Adverse Events to the Sponsor

The study site must report all SAEs, whether they are related to the device or procedure, to the Sponsor as soon as possible, but no later 72 hours of becoming aware of the SAE. The study site will report the SAE by entering the event into the EDC system via the Adverse Event eCRF, which will trigger an automated email to the Sponsor. Additional information, including the Investigator's assessment, may be added to the eCRF later; however, the study site must complete the AE eCRF within 72 hours of becoming aware of the SAE. If the Sponsor requires supporting documentation or other information, the Sponsor will contact the study site.

In the event of death, the Investigator must report all available information to the Sponsor.

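### The shared causality scale has no anchor for the study procedure, so a Visit 2A complication that precedes probe use can be rated 'Not related' and drop out of the procedure-related tables

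*Protocol*

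**What the plan says.** Protocol 12.1 first puts the procedure in scope: investigators have a "responsibility to assess the relationship between all AEs and the study procedure". It then supplies a single five-level table, whose entries "should be used in determining the relationship of an AE to a device, study procedure, or other causality". The wording of the levels that matter here is:

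- *Not related*: "Temporal sequence between device usage and the event is such that the relationship is unlikely". The *Causal relationship* row carries the same sentence.
- *Unlikely related* turns on timing relative to device usage, or on whether the subject's own "condition or concomitant therapy could have caused the AE".
- *Possibly related* has three alternatives: "Temporal sequence is relevant or the event abates upon device usage completion or the event cannot be reasonably explained by the patient's condition".

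The *Probably* level is also framed by device usage and its repetition.

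Protocol 12.2 lists relationship to the ablation device and "Relationship of AE to the study procedure" as two separate items. SAP 9.6 plans summaries of device-related events "as well as for AEs and SAEs related to the study procedure". It treats Unlikely, Possibly, Probably and Causal all as related. The procedure-related summaries are Tables 18 (AEs) and 19 (SAEs). Complications attributable to the procedure are a secondary endpoint (Protocol 6.2).

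**The concern.** Two relationship fields are useful only if they can give different answers: one for the device, one for everything else done to reach and treat the lesion. Here the second field has no definition of its own. The investigator is told to judge the procedure with sentences that ask about device usage.

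This matters because Protocol 4.0 argues for the endobronchial route largely on the expectation of fewer access complications, and procedure-attributable complications are a named endpoint. Tables 18-19 are the only planned tables of procedure-related events; the related-event tables for the first 30 days (20-21) cover the device only. If an event is attributed wrongly at the rating step, no other summary table restores the attribution.

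**Working it through.** No planned figure bears on this point, so the check compares texts.

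**Step 1. What each definition names (Protocol 12.1).**

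| Category | Names device usage | Names the procedure | Route that does not name the device | Counted as related (SAP 9.6) |
|---|---|---|---|---|
| Not related | yes | no | none | no |
| Unlikely related | yes | no | subject's condition or concomitant therapy | yes |
| Possibly related | yes, in one of three alternatives | no | relevant timing; not explained by the patient's condition | yes |
| Probably related | yes | no | none complete: the relevant-timing element does not name the device, but the rest does | yes |
| Causal relationship | yes | no | none (same sentence as Not related) | yes |

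Device usage appears in 5 of 5 definitions and the procedure in 0 of 5. Four of the five categories count as related, so entry to Tables 18-19 turns on one boundary: *Not related* against everything else.

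**Step 2. A complication close in time to probe use.** *Not related* is a test of timing, not of mechanism. An airway or anaesthetic complication in the same session as probe use has a close temporal sequence. It therefore does not naturally meet *Not related*, but it does meet the first alternative under *Possibly related*. Either *Possibly* or *Unlikely* keeps it in Tables 18-19.

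**Step 3. A complication before probe use.** Take an event at induction, CP-EBUS or navigation. It precedes device usage, so its timing argues against a link to the device, and it meets *Not related* as written. It can also meet *Possibly related*, because the patient's condition may not reasonably explain it. The two ratings fall on opposite sides of the SAP cut, and the text does not say which prevails. The *Unlikely* route through concomitant therapy is also unclear for anaesthesia, since Protocol 7.5 keeps anaesthetic components out of the concomitant medication record.

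**Step 4. Can such an event be in the analysis?** The Schedule of Assessments places CP-EBUS at Visit 2A. Because a positive node is an exclusion criterion, CP-EBUS evidently comes before ablation. That induction and navigation also come before it is an inference, as the procedure description is redacted. Protocol 12.2 starts AE collection at the start of the ablation procedure (Visit 2A), which can include these steps. Protocol 8.2.2 says the start of the ablation, which may not. The subject must also go on to be ablated: a patient whose ablation is never initiated is a screen failure (Protocol 7.6) and is outside the Full Analysis Set.

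**Step 5. Scale.** With 10 ablated subjects, one subject whose only procedure-related event is rated *Not related* changes the overall percentage by 1/10 = 10 percentage points. Tables 18-19 follow the Table 14 shell, which shows counts and percentages without confidence intervals. The documents give no count of such events.

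**The case against.** The strongest reply is that the procedure is expressly in scope and the SAP's cut is inclusive. The lead-in to the table covers the procedure, 12.2 gives it its own item, and a sensible investigator would read procedure for device when completing that item. *Possibly* and *Unlikely* have routes that do not name the device, and both count as related. Every AE and SAE appears in Tables 14-15 and Listing 29 whatever its rating, and with 10 subjects a reader can go through the listing. eCRF guidance, which is not among the documents, may settle the matter.

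Most of this stands, and it limits the point to events that precede probe use. A reader might infer more: that any bronchoscopy or anaesthesia complication fits *Not related*, that the procedure field will simply copy the device field, and that the procedure-related rate is therefore biased low. The documents support none of these. The first turns a timing test into a test of mechanism. The second is a guess about rater behaviour. The third ignores an inclusive cut under which an event put down to the patient's own condition, and so rated *Unlikely*, still counts as procedure-related.

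What the reply does not remove is the missing anchor. The tables and listing keep the event visible, but the endpoint reports its attribution. Relying on investigators to substitute a word that the protocol does not contain is not a definition.

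**Conclusion.** The point holds in a narrow form. The scale prescribed for procedure attribution has no procedure anchor. For complications before probe use it allows both *Not related* and *Possibly related*, so whether they appear in Tables 18-19 depends on which sentence the investigator applies. Complications close in time to probe use are mostly retained.

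The number of affected events and the net direction of any effect are unknown; under-counting is a risk for this subset, not a demonstrated bias. Each affected subject is worth up to 10 points at n = 10.

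The conclusion assumes that investigators apply the text as written, that no unseen eCRF guidance supplies a procedure anchor, and that events before probe use are collected under the wording of 12.2. The duplicated *Causal* sentence is a separate fault in the same table. Correcting it alone would still leave the procedure rating undefined.

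**What to change.** 1. In 12.1 and any eCRF guidance, keep device usage as the anchor for the device rating. For the procedure rating, use any part of the Visit 2A procedure: anaesthesia, bronchoscopy, CP-EBUS, navigation, probe placement and ablation.
2. In the same edit, replace the *Causal relationship* definition, which repeats *Not related*.
3. Reconcile the AE collection start in Protocol 8.2.2 with that in 12.2.
4. Before lock, have investigators confirm the procedure-relationship rating of all AEs with onset from Visit 2A through Visit 3 against the corrected wording. This step is needed because enrolment had already stopped when the SAP was written, so new text alone changes no rating already made. It must cover every rating: rechecking only those coded *Not related* could only raise the rate.
5. Footnote Tables 18-19 with the definition used and the fact that ratings were confirmed.

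The cost is one wording change and a short query round on 10 subjects. The procedure-related rate may change as a result.
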